8.5.3 Analysis of Other Endpoints

8.5.3.1 Efficacy Parameters

Clinical efficacy parameters will be analyzed descriptively in the Full Analysis Set.

For the dose escalation part of the trial, the secondary efficacy endpoint is BOR according to RECIST 1.1 per Investigator assessment. For a BOR of PR or CR, confirmation of the response according to RECIST 1.1 (Eisenhauer 2009) will be required. The response at each scheduled tumor assessment and the BOR will be listed for each subject. The ORR, defined as the proportion of subjects with BOR of PR or CR, will be tabulated by dose level.

For the dose-expansion part of the trial, the following secondary efficacy endpoints will be assessed:

- Duration of response, according to RECIST 1.1 and adjudicated by the IRC, will be calculated for each subject with a confirmed response and will be analyzed using the Kaplan-Meier method
- DCR, defined as the proportion of subjects with BOR of CR, PR, or SD for ≥ 12 weeks will be tabulated within each expansion cohort
- PFS and TTP time (according to RECIST 1.1 and adjudicated by the IRC) and OS time will be presented in listings and analyzed using the Kaplan-Meier method in each expansion cohort separately if the cohort enrolls the full planned number of subjects

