8.6 Interim and Additional Planned Analyses

Enrollment of expansion cohorts will not be stopped for the purpose of conducting their respective interim analyses but will stop if futility is met as specified.

Dose Escalation Part

In the dose-escalation part, the trial data will be evaluated before decision is made to go to the next dose level or to start with treatment in the expansion part.

Expansion Part

For all expansion cohorts except glioblastoma cohort, the endpoints in these interim analyses are ORR (confirmation is not required). For glioblastoma, the endpoint in the interim analysis will be DCR. There is no multiplicity adjustment is applied to the interim analyses. The decision rules at the interim analyses serve as guidance and are non-binding. In the absence of a control arm, outcomes in this single arm study have to be interpreted with caution, both at interim and final analyses.

CCI

HCC ascending-dose cohort

An interim analysis will be conducted 12 weeks after the final subject in the ascending-dose portion received their first dose.

If ≤ 6 responses are observed in the 30 subjects at the interim analysis, the enrollment into HCC second-line or sorafenib-intolerant cohort will be stopped. This decision criterion has 39% probability of rejecting the null hypothesis if the true response rate is 20% and 6% probability of rejecting the alternative hypothesis if the true response rate is 35%.

Enrollment of HCC second-line or sorafenib-intolerant cohort will not be stopped for the purpose of conducting this interim analysis but will stop if futility is met as specified.

HCC second-line or sorafenib-intolerant cohort

No interim analysis is planned.

NSCLC anti-PD-1 / anti-PD-L1 failure cohort

One interim analysis is planned for this cohort 12 weeks after the 40th subject in this cohort started treatment.

- If ≤ 2 responses are observed in the 40 subjects at the interim analysis, the enrollment will be stopped. This decision criterion has 32% probability of rejecting null hypothesis if the true response rate is 5% and 5% probability of rejecting alternative hypothesis if the true response rate is 15%.
- If 3 to 4 responses are observed at the interim analysis, the enrollment will be temporarily stopped until the first 40 subjects have completed tumor assessment at Week 24. After a review of the totality of data, including duration of response, DCR, and safety, the Sponsor will make a decision as to whether to resume the accrual.

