- If ≥ 5 responses are observed at the interim analysis, an additional 40 subjects will be enrolled. With 5 responses and using Bayesian principal, the posterior probability of true ORR being above 15% (alternative hypothesis) is approximately 41% and the posterior probability of true ORR being below 5% (null hypothesis) is approximately 2%.

Melanoma anti-PD-1 / anti-PD-L1 failure cohort

One interim analysis is planned for this cohort 12 weeks after the 30th subject in the cohort started treatment.

NSCLC second-line cohort

There is one planned interim analysis. The primary objective of the interim analysis is to assess the tolerability, safety, and preliminary antitumor activity.

The planned interim analysis will occur 12 weeks after the 30th subject in the cohort started treatment. If ≤ 4 responders are observed at the interim analysis, no further subjects will be enrolled into the NSCLC second-line cohort.

Pancreatic adenocarcinoma second-line cohort

One interim analysis is planned for this cohort 12 weeks after the 30th subject in the cohort started treatment.

CRC third-line cohort

One interim analysis is planned for this cohort 12 weeks after the 30th subject in the cohort started treatment.

SCCHN second-line cohort

One interim analysis is planned for this cohort 12 weeks after the 30th subject in the cohort started treatment.

TNBC second-line cohort

One interim analysis is planned for this cohort 12 weeks after the 30th subject in the cohort started treatment.

Ovarian post-platinum second-line cohort

One interim analysis is planned for this cohort 12 weeks after the 30th subject in the cohort started treatment.

Esophageal post-platinum second-line cohort

One interim analysis is planned for this cohort 12 weeks after the 30th subject in the cohort started treatment.

Glioblastoma second-line cohort

One interim analysis is planned for this cohort 12 weeks after the 30th subject in the cohort started treatment.

Cervical cohort

One interim analysis is planned for this cohort 12 weeks after the 30th subject in the cohort started treatment.

Additional Interim Analyses

In general, interim analyses at time points that are not specified in the protocol may be performed for internal planning purposes.

9 Ethical and Regulatory Aspects

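### In the two NSCLC cohorts gated by a response count, whether PFS, TTP and OS get a Kaplan-Meier estimate depends on the interim result

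*Protocol*

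**What the plan says.** Protocol 8.5.3.1 lists the secondary efficacy analyses for the expansion part.

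- PFS, TTP and OS are to be "analyzed using the Kaplan-Meier method in each expansion cohort separately if the cohort enrolls the full planned number of subjects". Whatever the enrolment, "OS time will be presented in listings", and the same holds for PFS and TTP. A cohort short of its target is therefore promised listings and nothing more for these three endpoints.
- In the same list, DCR "will be tabulated within each expansion cohort" and duration of response is analysed by Kaplan-Meier. Neither depends on enrolment.

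Protocol 8.6 makes enrolment depend on response.

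- In general: "Enrollment of expansion cohorts will not be stopped for the purpose of conducting their respective interim analyses but will stop if futility is met".
- NSCLC anti-PD-1/PD-L1 failure (planned 80): "If ≤ 2 responses are observed in the 40 subjects at the interim analysis, the enrollment will be stopped". With 3 or 4 responses, accrual is paused for a sponsor review of the wider data.
- NSCLC second-line (up to 80, randomised 1:1 to two doses): if at most 4 "responders are observed at the interim analysis, no further subjects will be enrolled into the NSCLC second-line cohort".
- HCC: at most 6 responses in the 30 ascending-dose subjects stops enrolment into the HCC second-line cohort.
- Status of these rules: "The decision rules at the interim analyses serve as guidance and are non-binding".

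**The concern.** Taken together, the two sections make the existence of a secondary-endpoint estimate a function of the trial's own results. A gated cohort with few responses stops, is then incomplete, and has no planned Kaplan-Meier curve. The same cohort with more responses fills and gets one. Anyone comparing PFS or OS across cohorts would find curves for gated cohorts that passed and only listings for those that failed.

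The condition also has no clear trigger. Many cohort sizes are stated as an upper limit. For HCC the target could be read as 30, 60 or 70, because the protocol counts 30 ascending-dose subjects, 30 second-line subjects and 40 optional further ones. Leaving that reading open until the data are in adds another reporting choice.

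**Working it through.** **Inputs.** Gates and their stated operating characteristics: Protocol 8.6. Cohort sizes and response rates: Protocol Synopsis (statistical methods) and 8.1.2.

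**Formula.** With at most r responders among n stopping the cohort, and true response rate p:

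P(stop) = Σ (x = 0 to r) C(n, x) pˣ (1 − p)ⁿ⁻ˣ

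**Step 1. Reproduce the protocol's own figures (8.6).**

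| Gate | Quantity | Recomputed | Stated |
|---|---|---|---|
| NSCLC failure, ≤ 2 of 40 | P(X ≥ 3), p = 5% | 0.323 | 32% |
| | P(X ≤ 2), p = 15% | 0.049 | 5% |
| HCC, ≤ 6 of 30 | P(X ≥ 7), p = 20% | 0.393 | 39% |
| | P(X ≤ 6), p = 35% | 0.059 | 6% |

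All four agree.

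**Step 2. Chance of losing Kaplan-Meier, if the rule is followed and the cohort is not yet full.**

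NSCLC failure at p = 5%: 0.95⁴⁰ + 40(0.05)(0.95³⁹) + 780(0.05²)(0.95³⁸) = 0.1285 + 0.2706 + 0.2777 = 0.677.

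| Cohort | Lower rate | Middle rate | Higher rate |
|---|---|---|---|
| NSCLC failure, ≤ 2 of 40 | 67.7% at ORR 5% | 22.3% at 10% | 4.9% at 15% |
| NSCLC second-line, ≤ 4 of 30 | 25.5% at ORR 20% | 3.0% at 30% | 0.15% at 40% |

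The second row rests on two assumptions: that responders are counted among 30 subjects, and that both dose groups share one ORR. Section 8.6 gives neither the denominator nor the dose split.

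If the pause at 3 to 4 responses in the NSCLC failure cohort were never lifted, the relevant probability would be P(X ≤ 4 of 40): 95% at ORR 5% and 26% at 15%. That is an upper limit for this cohort.

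**Step 3. Which cohorts are exposed.**

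- Melanoma, pancreatic, CRC, SCCHN, TNBC, ovarian, esophageal, glioblastoma and cervical: each plans 30 subjects, and its interim is timed from the 30th subject's start of treatment. No stopping threshold is visible. Enrolment is complete when the interim is read, so it cannot cut the cohort short.
- HCC ascending-dose, 1200 mg: its 30 subjects are all enrolled when its gate is read, so the gate does not make it incomplete.
- HCC second-line: Protocol 8.1.2 has the first 30 enrolled only if the gate is passed, while 8.6 describes stopping an enrolment already under way. Only under the second description can a partly filled cohort lose its curves.

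**Step 4. Does sample size justify the condition?** A stopped NSCLC failure cohort has at least 40 subjects, more than the 30-subject cohorts that do get Kaplan-Meier. At an observed proportion of 20%, the exact 95% interval is 0.091 to 0.356 with 8 of 40 (width 0.27). With 6 of 30 it is 0.077 to 0.386 (width 0.31), which matches Table 12. Kaplan-Meier duration of response is planned without the condition in responders alone, a smaller group still.

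**Step 5. Bias within a cohort that continues.** As an illustration for NSCLC failure at ORR 5%, assume exponential PFS with a median of 2 months in non-responders and 6, 9 or 18 months in responders. These medians are not in the documents. Simulated 6-month PFS in continuing cohorts is 15.2%, 16.1% or 17.2%, against true values of 14.4%, 15.1% or 15.8%. The excess is 0.8, 1.0 or 1.4 points.

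**The case against.** The restriction is prespecified and concerns secondary, descriptive endpoints. A failing cohort is not hidden: the confirmed ORR with an exact interval (Protocol 8.5.2.2), DCR and Kaplan-Meier duration of response carry no enrolment condition, and 8.5.1 has all data listed. The rules are non-binding and enrolment runs on during the interim, so a cohort may fill regardless. All of this stands. It limits the consequence but does not explain why three endpoints are treated differently.

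A second objection is that other documents may settle the matter. SAP section 6 says that plans for the by-cohort interim and primary analyses and for the CSR were developed separately. They were not available here and may have dropped the condition. SAP 6.1 also says that the results are already in a CSR approved in March 2021. The supplied SAP applies Kaplan-Meier to PFS and OS without the condition (14.3, 14.4). However, its efficacy analyses cover cervical cancer only (section 14), it plans no TTP analysis, and 6.1 cancels the work. It does not lift the protocol's condition.

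Three stronger readings are tempting but unsupported:

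- **That every expansion cohort is at risk.** Step 3 shows that the nine 30-subject cohorts cannot be cut short by their interim.
- **That HCC has a 61% chance of losing its curves at ORR 20%.** That figure (1 − 0.393) is the chance that the gate is not passed. It is read on an ascending-dose cohort that is already full; and if the second-line cohort never opens, no estimate is lost.
- **That the survival results are biased upward by a material amount.** Each cohort is analysed separately (8.5.1), so omitting one curve does not distort another, and the excess in step 5 is small.

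Nor is a loss of Kaplan-Meier at one subject short established: where a size is an upper limit, the target is undefined.

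**Conclusion.** The point holds for the two NSCLC cohorts with a response gate, most clearly the anti-PD-1/PD-L1 failure cohort. Following the protocol as written can remove the Kaplan-Meier estimate of PFS, TTP and OS because responses were few. The chance is 68% against 5% (ORR 5% against 15%) in the failure cohort, and about 26% against 0.2% (ORR 20% against 40%) in the second-line cohort. These figures assume that the non-binding rule is followed and that enrolment has not already filled; the second pair also needs the two assumptions in step 2. A partly enrolled HCC second-line cohort is a further possibility, with no probability attached.

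The harm is selective availability of survival estimates between cohorts. The protocol wording and the binomial figures are firm. Whether estimates were in fact withheld cannot be judged from the documents supplied. This is a cheap improvement and no threat to the primary analysis.

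**What to change.** In Protocol 8.5.3.1, delete the closing condition on complete enrolment. State instead that Kaplan-Meier PFS, TTP and OS, with 95% confidence intervals and numbers at risk, will be reported on the Full Analysis Set for every expansion cohort that treated subjects, and that cohorts stopped early will be flagged. Carry the same sentence into the by-cohort and CSR analysis plans if they repeat the condition.

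The cost is one sentence and a few standard tables. Survival follow-up is already planned (7.1.4.3) and the listings are already promised, so no new data are needed, and no sample size, alpha or power changes. The downside is wide intervals in small cohorts, which the flag and the numbers at risk make plain.

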8.5.3.2 Pharmacokinetic Profile

Plasma concentrations of MSB0011359C will be determined by a validated method at the times listed in Schedules of Assessments (refer to Table 1 and Table 2).

The following PK parameters will be estimated and reported in the PK Analysis Set:

- AUC_{0-t} (dose escalation portion, HCC, and NSCLC biomarker cohorts only): Area under the concentration-time curve from the time of dosing to the time of the last observation (calculated by linear trapezoidal summation).
- $AUC_{0-\infty}$ (dose escalation portion, HCC, and NSCLC biomarker cohorts only): Area under the concentration-time curve from the time of dosing extrapolated to infinity (calculated by the linear trapezoidal summation and extrapolated to infinity using C_{last}/λ_z).
- λ_z (dose escalation portion, HCC, and NSCLC biomarker cohorts only): Terminal elimination rate constant. The value of λ_z is determined from the slope of the regression line of log (concentration) vs. time with the following constraints: (i) there must be at least 3 consecutive measurable concentrations, (ii) all concentrations must be declining with time, and (iii) the correlation coefficient (r) of regression must be ≥ 0.95 .
- C_{max} : Maximum serum concentration observed postdose.
- C_{min} : Minimum serum concentration observed postdose.
- t_{max} (dose escalation portion, HCC, and NSCLC biomarker cohorts only): Time at which the C_{max} occurs.
- $t_{1/2}$ (dose escalation, HCC, and NSCLC biomarker cohorts only): Elimination half-life, determined as $0.693/\lambda_z$.

The PK parameters will be summarized using descriptive statistics. Individual as well as mean concentration-time plots will be depicted.

Unresolved missing data may be imputed when the analysis integrity is affected. The conservative principle will be used for data imputation.

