ADA = antidrug antibody; AE = adverse events; ANA = antinuclear antibody; β-HCG = β-human chorionic gonadotropin; CT = computed tomography; DLT = dose-limiting toxicity; ECG = electrocardiogram; ECOG PS = Eastern Cooperative Oncology Group Performance Status; EORTC QLQ-BN20 = European Organisation for Research and Treatment of Cancer Quality of Life Questionnaire Brain Module; EORTC QLQ-C30 = European Organisation for Research and Treatment of Cancer Quality of Life Questionnaire Core instrument; EORTC QLQ-CX24 = European Organisation for Research and Treatment of Cancer Quality of Life Questionnaire Cervical Cancer Module; EORTC QLQ-OES18 = Organisation for Research and Treatment of Cancer Quality of Life Questionnaire Oesophageal Module; EORTC QLQ-HCC18-M = European Organisation for Research and Treatment of Cancer Quality of Life Questionnaire Hepatocellular Carcinoma Module – Modified; EORTC QLQ-OV28 = European Organisation for Research and Treatment of Cancer Quality of Life Questionnaire Ovarian Module; EoT = End-of-Treatment; FHSI-8 = FACT [Functional Assessment of Cancer Therapy] Hepatobiliary Symptom Index – 8 questions; FSH = follicle-stimulating hormone; HBV = hepatitis B virus; HCV = hepatitis C virus; Hgb = hemoglobin; HIV = human immunodeficiency virus; IMP = investigational medicinal product; IV = intravenous; MRI = magnetic resonance imaging; NSCLC-SAQ = Non-small Cell Lung Cancer Symptom Assessment Questionnaire; PD = progressive disease; PGIS = Patient Global Impression of Severity; PK = pharmacokinetics; RECIST = Response Evaluation Criteria in Solid Tumors; RF = rheumatoid factor; SMC = Safety Monitoring Committee; TGFβ = transforming growth factor beta; TSH = thyroid-stimulating hormone; T4 = free thyroxine.

After at least 50 subjects across the dose escalation and all expansion cohorts have been evaluated for safety by the SMC, with appropriate SMC safety recommendation and if the Sponsor considers PK characterization adequate, then Day 2, 8, and 22 visits may be skipped. Also, the Safety Follow-up visit (10 weeks after the last dose) may be conducted by phone without the scheduled assessments.

Unless stated otherwise in a footnote, all procedures and samples should occur prior to trial drug administration.

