- a A time window of up to 3 days before or 1 day after the scheduled visit day (-3 / +1 days) will be permitted for all procedures (except Day 2 and the Day 44-50 visit). The bi-weekly 14-day schedule should be strictly adhered to, returning to the target date even if the previous visit was off schedule. If any Screening procedures are conducted within 3 days prior to Day 1 of trial treatment (Week 1, Day 1), the assessments scheduled on Week 1, Day 1 do not need to be repeated except for the evaluation of AEs and concomitant medications. The Day 44-50 visit is to accommodate collection of tumor biopsy material and associated PK and CCI sampling (see Table 3); the Day 44-50 visit is only to occur if the tumor biopsy and associated PK sampling cannot be performed at the Day 43 visit.
- b The Day 2 PK and biomarker samples must be drawn at least 24 hours after the Day 1 end of infusion, preferably > 30 hours after end of infusion. The exact time of each draw must be recorded. A protocol deviation will be defined by a sample not being drawn. In the backfill cohorts an additional sample can optionally be drawn at 3 to 5 days after the initiation of the infusion and 1 optional PK sample can be taken any time during days 10 to 12. The exact time must be recorded.
- c If another antineoplastic therapy is administered before the end of this 28-day period, the 28-Day Safety Follow-up visit should be conducted, if possible, prior to the start of this new therapy. If it is known to the Investigator at the time of the End-of-Treatment visit that the subject will start new treatment within 28 days of last treatment or they will be unable to return within 28 days of last treatment, assessments associated with the 28-Day Safety Follow-up visit may be conducted at the End-of-Treatment visit.
- d Blood samples for PK analysis should be drawn on Day 1 prior to dosing, immediately after completion of the infusion, and 4 hours after the start of the infusion. A sample to be taken at 8 to

12 hours after the start of the infusion is optional in the backfill cohorts. The exact time of each draw must be recorded. A protocol deviation will be defined by a sample not being drawn.

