3.2.2 Pharmacokinetics / CCI

CCI

A brief summary of PK and PK / CCI is as follows:

[figure not shown]
[figure not shown]
- The predicted human terminal half-life ($t_{1/2}$) for MSB0011359C is approximately 6 days
- Simulations predict that a 1 mg/kg dose will provide an average exposure of approximately 7 µg/mL in humans
- Based on PK / CCI modeling and human projections:
 - At a human dose of 0.1 mg/kg, 95% PD-L1 total occupancy at maximum serum concentration observed postdose (C_{max}) is expected in PBMCs, providing approximately 60% total occupancy in tumor
 - At a human dose of 1.0 mg/kg, more than 95% of PD-L1 total occupancy at C_{max} is expected in PBMCs and tumor
 - At a human dose of 1.0 mg/kg, 20% effect is projected in tumor regression in the PK / CCI model compared with 95% at 7.5 mg/kg

- Human pharmacokinetics indicate a dose of 7.5 mg/kg and higher (range 4 to 20 mg/kg), on a biweekly schedule is needed to achieve full efficacy

-

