5.1.2 Trial Medication Administration and Schedule

Subjects will receive IV infusion of MSB0011359C over 1 hour (-10 minutes / +20 minutes, that is, over 50 to 80 minutes) once every 2 weeks. Subjects enrolled in the 30 mg/kg and 2400 mg flat-dose cohorts may have a total infusion time of up to 120 minutes. In order to mitigate potential infusion-related reactions, premedication with an antihistamine and with paracetamol (acetaminophen) (for example, 25-50 mg diphenhydramine and 500-650 mg paracetamol [acetaminophen] IV or oral equivalent) approximately 30 to 60 minutes prior to each dose of MSB0011359C is mandatory for the first 2 infusions and is optional and at the discretion of the Investigator after the second infusion (premedication is optional for all infusions for subjects in the NSCLC biomarker cohort being treated at the US NCI). If Grade ≥ 2 infusion reactions are seen during the first two infusions, premedication should not be stopped. Steroids as premedication are not permitted.

The trial treatment schedules are provided in the Schedules of Assessments (see [Table 1](#) and [Table 2](#)).

The formulation and packaging information of MSB0011359C is provided in Sections 6.1 and 6.6.

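### AUC is integrated with straight lines over a log-linear decline: about 4% too high as scheduled, about 20% only if Day 2 and Day 8 samples are missing

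*Protocol*

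**What the plan says.** Protocol Section 8.5.3.2 defines AUC0-t as "calculated by linear trapezoidal summation" and builds AUC0-∞ the same way, adding the last concentration divided by λz. No logarithmic rule is given for the falling part of the curve. Both are reported for the "dose escalation portion, HCC, and NSCLC biomarker cohorts only".

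The same section takes λz from the "slope of the regression line of log (concentration) vs. time". It requires at least three consecutive measurable concentrations, all falling with time, and a correlation coefficient r of at least 0.95.

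Protocol Table 3 gives the three AUC groups the same core cycle-1 times. On Day 1, samples are taken "prior to dosing, immediately after completion of the infusion, and 4 hours after the start of the infusion" (footnote d), and further samples follow on Days 2, 8 and 15. On Day 2, footnote b says: "The Day 2 PK and biomarker samples must be drawn at least 24 hours after the Day 1 end of infusion". Section 5.1.1.1 adds three samples (8 to 12 hours, 3 to 5 days, 10 to 12 days) in the 0.1 and 0.3 mg/kg cohorts and the added PK subjects at 1 to 20 mg/kg. Table 3 labels these optional.

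The note to Table 2 and the note ending Section 7.1.2.2 cover the expansion phase. Once at least 50 subjects have been reviewed, with a safety recommendation from the Safety Monitoring Committee, and if the sponsor judges the PK sufficiently characterised, "then Day 2, 8, and 22 visits may be skipped". Neither note exempts the HCC or NSCLC biomarker cohorts.

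The SAP supplied covers a cancelled report addendum. Its Section 16.1.3 lists only Ctrough and CEOI, so it does not touch the AUC rule.

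**The concern.** The plan assumes a log-linear decline when it estimates λz, then integrates that decline with straight lines. On a falling exponential the error is always upward, and it grows quickly with the gap between samples. The size of the error therefore depends on who was sampled when, not only on exposure.

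Two consequences follow. First, Section 5.1.1.1 looks to the 30 mg/kg and 2400 mg cohorts for insight into dose proportionality. Those subjects have core sampling, while low-dose and backfill subjects may have the extra samples, so the bias is not the same on both sides of that comparison. Second, if Day 2 and Day 8 were dropped for some HCC or NSCLC biomarker subjects, their AUC would be inflated much more. That could read as a real difference in exposure, and if skipping began during enrolment it would also divide subjects within a cohort.

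Separately, r is negative for any falling curve. Read literally, the criterion r ≥ 0.95 can never be met, which would leave λz, half-life and AUC0-∞ unreportable.

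**Working it through.** The documents give no AUC value or bias figure to reproduce, so the check is a direct calculation.

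**Inputs**
- Half-life: the predicted value "for MSB0011359C is approximately 6 days" (Protocol Section 3.2.2), so λ = 0.693/6 = 0.1155 per day. The range 4 to 8 days is an assumption.
- Interval: 14 days, from dosing "once every 2 weeks" (Section 5.1.2).
- Scheduled times: 0, 1 h, 4 h, 25 h (Day 2), 7 d (Day 8), 14 d (Day 15).
- Shape: 1-hour infusion, then mono-exponential decline (an assumption).

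**Formulas.** For a falling interval of length h from C1 to C2, the linear area is h(C1 + C2)/2 and the true area is (C1 − C2)/λ. Their ratio is x·coth(x) with x = λh/2, which is always above 1.

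**Numbers, 6-day half-life.** In relative units the concentrations are 0.998 (1 h), 0.983 (4 h), 0.889 (25 h), 0.447 (Day 8) and 0.199 (Day 15).

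| Interval | Length (days) | Linear | True |
|---|---|---|---|
| 0 to 1 h | 0.04 | 0.021 | 0.021 |
| 1 to 4 h | 0.13 | 0.124 | 0.124 |
| 4 to 25 h | 0.88 | 0.819 | 0.818 |
| 25 h to Day 8 | 5.96 | 3.978 | 3.828 |
| Day 8 to Day 15 | 7.00 | 2.259 | 2.143 |
| **Total, as scheduled** | | **7.201** | **6.934** |

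Ratio 7.201/6.934 = 1.038. Nearly all the excess comes from the two long gaps.

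Without Days 2 and 8, the last three rows become one interval of 13.83 days: linear 8.177, true 6.790. The total is 8.321/6.934 = 1.200. Against scheduled sampling this is 1.200/1.038 = 1.16.

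**Bias in AUC over 14 days, linear rule, mono-exponential**

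| Half-life | As scheduled | With extra optional samples | Days 2 and 8 missing |
|---|---|---|---|
| 4 d | +8.0% | +2.1% | +42.7% |
| 6 d | +3.8% | +1.0% | +20.0% |
| 8 d | +2.2% | +0.6% | +11.5% |

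The extra samples are placed at 10 h, day 4 and day 11. Across their windows the 6-day figure runs from +1.0% to +1.5%. Moving the Day 2 sample to 31 h gives +3.6% as scheduled. For AUC0-∞ at 6 days the three figures are +3.1%, +0.8% and +16.0%.

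**Effect of linear-up/log-down.** Under a mono-exponential curve the bias is zero for every sampling scheme. As a sensitivity check, take a bi-exponential curve with an assumed 40% fast phase of 1-day half-life and a 6-day terminal half-life:

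| Rule | As scheduled | With extra samples | Days 2 and 8 missing |
|---|---|---|---|
| Linear | +10.4% | +2.9% | +59.3% |
| Log-down | +4.1% | +1.2% | +20% |

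The log rule removes most of the error but cannot replace samples that were not taken.

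**Does the three-point rule protect?** No. With Days 2 and 8 missing, end of infusion, 4 h and Day 15 are still three falling points, so AUC0-∞ could be computed.

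**The case against.** A reader might infer that the design builds in fuller sampling for dose escalation than for the expansion cohorts with AUC, and hence a spurious exposure gap of about 16%. The documents do not support that. The core times are the same in all three groups, so as planned the bias of about 4% is shared and largely cancels. The skip option is conditional, and one condition is the sponsor's own judgement of the PK. Table 3 does not repeat the permission, and its footnotes treat an undrawn PK sample as a deviation. Nothing shows that skipping was used in the HCC or NSCLC biomarker cohorts.

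It is also fair to say that no AUC threshold, test or formal comparison of expansion with escalation is specified, and that PK parameters are only summarised. The exposure-response aim in the synopsis belongs to the second-line NSCLC cohort, where AUC is not planned. The plan used for the clinical study report is a separate document that is not available here, so the AUC method finally applied is unknown. The r criterion was presumably meant as a magnitude.

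All of this stands, and it limits the size of the point. It does not justify the rule itself: the section treats the decline as log-linear and then ignores that. Nor does it provide for AUC when the Day 2 or Day 8 sample is missing.

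**Conclusion.** The point holds, and it is minor. As scheduled, the linear rule overstates AUC over 14 days by about 4% in all AUC cohorts (about 2% to 8% for half-lives of 8 to 4 days). For low-dose and backfill subjects with the extra samples it is about 1%. The difference that enters a dose-proportionality reading is therefore about 3 percentage points, or about 7 under the bi-exponential assumption. It makes higher-dose cohorts on core sampling look slightly more exposed. The figure of about 20% (about 11% to 43%) is conditional on the skip option having been applied to HCC or NSCLC biomarker subjects.

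These sizes rest on a half-life that is a pre-trial prediction, on assumed curve shapes, and on taking AUC over the first dosing interval, which Section 8.5.3.2 does not name. The direction of the bias needs only a convex decline. AUC is a descriptive secondary endpoint, and no decision in the plan turns on it.

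**What to change.** In Protocol Section 8.5.3.2, or in the plan that governs the PK report:

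1. Specify linear trapezoids while concentrations rise and logarithmic trapezoids while they fall, for AUC0-t and AUC0-∞ in all AUC cohorts, and name the dosing interval.
2. State that AUC is flagged or not reported when the Day 2 or Day 8 sample is missing. The log rule alone is not enough if the decline is bi-exponential.
3. Write the λz criterion as |r| ≥ 0.95, equivalently r² ≥ 0.9025.

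The log-down rule is a standard option in the named PK software and no new data are needed. The cost is not zero. The full escalation analysis was complete when the 2400 mg cohort was added (Section 5.1.8), and the clinical study report was approved in March 2021 (SAP Section 6.1). AUC values already reported would have to be recomputed from existing concentrations so that methods are not mixed across cohorts. Failing that, the report should state the rule used and which samples each AUC rests on.
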